10.4. Quality assurance

To ensure compliance with GCP and all applicable regulatory requirements, GSK may conduct a quality assurance audit. Regulatory agencies may also conduct a regulatory inspection of this study. Such audits/inspections can occur at any time during or after completion of the study. If an audit or inspection occurs, the investigator and institution agree to allow the auditor/inspector direct access to all relevant documents and to allocate his/her time and the time of his/her staff to the auditor/inspector to discuss findings and any relevant issues.

10.5. Posting of information on publicly available clinical trial registers and publication policy

Study information from this protocol will be posted on publicly available clinical trial registers before enrolment of subjects begins.

Summaries of the results of GSK interventional studies (phase I-IV) are posted on publicly available results registers within 12 months of the primary completion date for studies of authorised vaccines and 18 months for studies of non-authorised vaccines.

GSK also aims to publish the results of these studies in the searchable, peer reviewed scientific literature. Manuscripts are submitted for publication within 24 months of the last subject's last visit. At the time of publication, this protocol will be fully disclosed.

10.6. Provision of study results to investigators

Where required by applicable regulatory requirements, an investigator signatory will be identified for the approval of the study report. The investigator will be provided reasonable access to statistical tables, figures, and relevant reports and will have the opportunity to review the complete study results at a GSK site or other mutually-agreeable location.

GSK Biologicals will also provide the investigator with the full summary of the study results. The investigator is encouraged to share the summary results with the study subjects, as appropriate.

11. COUNTRY SPECIFIC REQUIREMENTS

Not applicable.

1. DOCUMENT HISTORY

| Date | Description | Protocol Version |
|-------------|---------------|---------------------|
| 12-OCT-2017 | first version | Final - 02-FEB-2016 |

2. STUDY DESIGN

n = Total number of subjects, PRE = Blood sample to be collected before vaccination, PD7 = Blood sample to be collected 7 days after vaccination, PD30 = Blood sample to be collected 30 days after vaccination

- Experimental design: Phase IV, open-label, non-randomised, multi-centric, multi-country study with a single group.
- Duration of the study: Approximately one month per subject, starting from the administration of the challenge dose.
 - Epoch 001: Primary starting at Visit 1 (Day 0) and ending at Visit 3 (Day 30).

Study group:

- LTFU: Subjects who received 3 or 4 doses of *Engerix-B* 20 to 30 years ago.

Study group and epoch foreseen in the study

| Study Group | Number of subjects | Age (Min/Max) * | Epoch |
|-------------|--------------------|---------------------|-----------|
| | | | Epoch 001 |
| LTFU | Approximately 100 | 40 years – 60 years | x |

*Age at visit 1

Study group and treatment foreseen in the study

| Treatment Name | Vaccine Name | Study Group |
|----------------|--------------|-------------|
| | | LTFU |
| Engerix-B | HBV | x |

- Control: uncontrolled.
- Vaccination schedule: A single dose of *Engerix-B* will be administered to all subjects at Visit 1 (Day 0).
- Treatment allocation: Non-randomised.
- Blinding: Open label.
- Sampling schedule: Blood samples will be taken from all subjects in order to evaluate the immunogenicity endpoints. The following blood samples will be taken at each study visit (Visit 1, Visit 2 and Visit 3):
 - Three heparinised tubes of whole blood, of approximately 9 ml each, will be sampled for the assessment of memory B cells and T cells.
 - One tube of approximately 5 ml of blood will be taken, from which approximately 1.7 ml of serum will be extracted for the measurement of antibodies.
- Type of study: self-contained.
- Data collection: Electronic Case Report Form (eCRF).

The following group names will be used for the statistical analyses:

| Group order in tables | Group label in tables | Group definition for footnote |
|-----------------------|-----------------------|---------------------------------------|
| 1 | HBV | HBV : Engerix-B challenge dose |

| Sub-group order in tables | Sub-group label in tables | Sub-group definition for footnote |
|---------------------------|---------------------------|-----------------------------------|
| 1 | 40-50 Y | 40-50 years old subjects |
| 2 | 51-60 Y | 51-60 years old subjects |

3. OBJECTIVES

Primary:

- To assess the persistence of immunity to hepatitis B in terms of anti-HBs anamnestic response to an *Engerix-B* challenge dose, in adult subjects vaccinated with three or four doses of *Engerix-B* 20 to 30 years ago.

Secondary:

- To assess the persistence of immunity to hepatitis B in terms of Geometric Mean Concentrations (GMCs), seropositivity rates, seroprotection rates, and percentage of subjects with anti-HBs antibody concentrations ≥ 100 mIU/ml, before or after the *Engerix-B* challenge dose, in subjects vaccinated with three or four doses of *Engerix-B* 20 to 30 years ago
- To assess the persistence of immunity to hepatitis B in terms of T cell and memory B cell mediated immune responses specific to hepatitis B surface antigen, before and after the *Engerix-B* challenge dose, in adult subjects vaccinated with three or four doses of *Engerix-B* 20 to 30 years ago
- To evaluate the safety and reactogenicity of *Engerix-B* challenge dose in terms of solicited symptoms, unsolicited symptoms and serious adverse events (SAEs)

4. ENDPOINTS

Primary:

- Persistence of immunity to hepatitis B in adult subjects vaccinated with three or four doses of *Engerix-B* 20 to 30 years ago
- Percentage of adult subjects with an anamnestic response 7 days and 30 days after the challenge dose

Secondary:

- Persistence of immunity to hepatitis B in adult subjects vaccinated with three or four doses of *Engerix-B* 20 to 30 years ago
- Percentage of adult subjects with anti-HBs antibody concentrations ≥ 6.2 mIU/ml, ≥ 10 mIU/ml and ≥ 100 mIU/ml, at the pre-challenge dose time-point and Day 7 and Day 30 post-challenge dose time-points.
- Anti-HBs antibody concentrations, at the pre-challenge dose time-point and Day 7 and Day 30 post-challenge dose time-points.
- Hepatitis B specific memory B cell-mediated immune responses (frequency of HBs-specific memory B cells) at the pre-challenge dose time-point and Day 7 and Day 30 post-challenge dose time-points.
- Hepatitis B Specific T cell-mediated immune responses (frequency of HBs-specific CD4 T-lymphocytes) at the pre-challenge dose time-point and Day 7 and Day 30 post-challenge dose time-points.

5. ANALYSIS SETS

5.1. Definition

Two cohorts are defined for the purpose of analysis

- Total Vaccinated Cohort(TVC) will include all subjects who received the challenge dose
- ATP cohort for analysis of immunogenicity (ATP Immunogenicity)- will include all evaluable subjects (i.e. those meeting all eligibility criteria, complying with the procedures defined in the protocol, with no elimination criteria during the study) who have received the challenge dose and for whom data concerning immunogenicity endpoint measures at pre-challenge (Visit 1) and one-month post-challenge (V3) are available. The interval between Visit 1 and Visit 3, considered for inclusion of a subject in the ATP cohort for analysis of immunogenicity will be 21-48 days

5.2. Criteria for eliminating data from Analysis Sets

Elimination codes are used to identify subjects to be eliminated from analysis. Detail is provided below for each sets.

5.2.1. Elimination from Total Vaccinated Cohort

Code 1030 (Study vaccine not administered at all) and code 900 (invalid informed consent or fraud data) will be used for identifying subjects eliminated from TVC

5.2.2. Elimination from ATP cohort for analyses of Immunogenicity

5.2.2.1. Excluded subjects

A subject will be excluded from the ATP analysis under the following conditions

| Code | Condition under which the code is used | | | |
|------|--|---------------|-------|---------------|
| 1030 | Study vaccine not administered at all | | | |
| 1040 | Administration of concomitant vaccine(s) forbidden in the protocol (see also eligibility criteria) | | | |
| 1070 | Administration not according to protocol for reason specified by the investigator, other than side, site and route. | | | |
| 1080 | Vaccine has been administered (effective treatment number) despite a temperature deviation qualified by Status QA GMP NON Use. | | | |
| 1090 | Vaccine has been administered (effective treatment number) out of the expiration date at the time of administration. | | | |
| 2010 | Protocol violation linked to the inclusion/exclusion criteria including age and excluding codes mentioned below. | | | |
| | 
 
 DOB	VAC_1	40-60 (years)	
 
 | DOB | VAC_1 | 40-60 (years) |
| DOB | VAC_1 | 40-60 (years) | | |

| Code | Condition under which the code is used | | | | | | | | | | | | | | | | | |
|---|---|--------------|--------------------------------|----------------|-------------------------------------|--|---|----------|------------|---------|----------------|-------------------------------------|--|----|---------|--------------------------------|--|--|
| 2040 | Administration of any medication forbidden by the protocol. | | | | | | | | | | | | | | | | | |
| 2050 | Underlying medical condition forbidden by the protocol. | | | | | | | | | | | | | | | | | |
| 2060 | Concomitant infection related to the vaccine which may influence immune response | | | | | | | | | | | | | | | | | |
| 2070 | Concomitant infection not related to the vaccine which may influence immune response (e.g. Hepatitis infection in a lyme study) | | | | | | | | | | | | | | | | | |
| 2090 | 
Blood sample taken but: noncompliance with blood sampling schedules (dates of BS not corresponding to adapted protocol intervals or unknown BS/vaccination dates)
 
 
 VAC_1	SER_2	5-12(days)	
 
 VAC_1	SER_3	21-48 (days)	
 
 | | | | | | VAC_1 | SER_2 | 5-12(days) | VAC_1 | SER_3 | 21-48 (days) | | | | | | |
| VAC_1 | SER_2 | 5-12(days) | | | | | | | | | | | | | | | | |
| VAC_1 | SER_3 | 21-48 (days) | | | | | | | | | | | | | | | | |
| 2100 | 
Serological results not available for antigens POST vaccination (including lost samples, blood sample not done, unable to test, and absence of parallelism).
 
Please specify the applicable rule:
 
 elimination code if ALL are missing
 
 elimination code if at least ONE is missing
 
  
 Schedule Leave blank if applicable for all schedules	Activity	Visit	Antigen	Lab variant ID	Seroprotection level (if available)	
   
 	30	Visit 3	Anti-HBS Results not available			
  
 | | | | | | Schedule Leave blank if applicable for all schedules | Activity | Visit | Antigen | Lab variant ID | Seroprotection level (if available) | | 30 | Visit 3 | Anti-HBS Results not available | | |
| Schedule Leave blank if applicable for all schedules | Activity | Visit | Antigen | Lab variant ID | Seroprotection level (if available) | | | | | | | | | | | | | |
| | 30 | Visit 3 | Anti-HBS Results not available | | | | | | | | | | | | | | | |
| 2120 | Obvious incoherence, abnormal serology evolution or error in data (incoherence between CRF and results, wrong sample labelling) | | | | | | | | | | | | | | | | | |

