6.3. Immunogenicity

6.3.1. Analysis of immunogenicity planned in the protocol

The primary analysis on the response to the challenge dose will be performed on the ATP cohort for analysis of immunogenicity. If the percentage of subjects excluded from the ATP cohort for immunogenicity is more than 5%, a second analysis based on the TVC will be performed to complement the ATP analysis of immunogenicity. The immunogenicity analysis based on the TVC will include subjects for whom immunogenicity data are available. All the immunogenicity analysis will be performed as a whole group and by age stratification. The age stratification will be 40-50 years and 51-60 years.

The following analyses will be performed:

- The percentage of subjects with anti-HBs antibody concentrations ≥ 6.2 mIU/ml, ≥ 10 mIU/ml, ≥ 100 mIU/ml, ≥ 1000 mIU/ml with exact 95% CIs will be calculated at the pre-challenge dose time-point, Day 7 and Day 30 post-challenge dose time-points.
- The percentage of subjects who mount an anamnestic response to the challenge dose, one month after vaccination, will be tabulated with exact 95% CI as a whole and according to their seroprotection status at pre-challenge time-point (anti-HBs antibody concentrations \leq or ≥ 10 mIU/ml).
- GMCs with 95% CI will be calculated for anti-HBs antibodies at the pre-challenge dose time-point, Day 7 and Day 30 post-challenge dose time-points.
- The distribution of anti-HBs antibody concentrations will be displayed using reverse cumulative distribution curve (RCC) at the pre-challenge dose time-point and Day 30 post-challenge dose time-point.
- Relationship between pre-challenge dose time-point and Day 30 post-challenge dose time-point results will be presented by regression line graph.
- CMI responses in terms of frequency of HBs-specific CD4⁺ T-lymphocytes and frequency of HBs-specific memory B cells at Day 0, Day 7 and Day 30 (for subjects who received a challenge dose) will be evaluated.
- The percentage of subjects with anti-HBs concentrations ≥ 6.2 mIU/ml, ≥ 10 mIU/ml and ≥ 100 mIU/ml (with 95% CI) at the Day 7 and Day 30 post-challenge dose time-points will be tabulated in relation to their pre-challenge dose status (overall, < 10 mIU/ml and ≥ 10 mIU/ml).
- The percentage of subjects (with 95% CI) who mount an anamnestic response will be calculated and in relation to their pre-challenge dose status (< 10 mIU/ml and ≥ 10 mIU/ml)

Exploratory Analysis:

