11.2.4. Immunogenicity

- Seronegative subjects:
 - Subjects with anti-HBs antibody concentration < 6.2 mIU/ml
- Seropositive subjects:
 - Subjects with anti-HBs antibody concentration \geq 6.2 mIU/ml
- Seroprotected subjects:
 - Subjects with anti-HBs antibody concentration \geq 10 mIU/ml
- Anamnestic response to the challenge dose is defined as:
 - At least (i.e. \geq) 4-fold rise in one month post-vaccination anti-HBs antibody concentrations in previously seropositive subjects.
 - In previously seronegative subjects, anti-HBs antibody concentrations \geq 10 mIU/ml at one month post-challenge dose time-point.
- Amplitude of anamnestic response is the change in fold value from pre-challenge dose time-point to one month post-challenge dose.
- The Geometric mean antibody concentrations (GMCs) calculations will be performed by taking the anti-log of the mean of the \log_{10} concentration transformations. All subjects will be considered. Subjects whose antibody concentrations are below the cut-off of the assay will be given an arbitrary value of half the cut-off for the purpose of GMC calculation Note that as per assay specification, results between the assay cut-off of 6.2 mIU/ml and 7.65 mIU/ml (= Lower limit of Quantification) will be quantified as 6.2 mIU/ml.

- For a given subject and a given immunogenicity measurement, missing or non-evaluable measurements will not be replaced. Therefore, an analysis will exclude subjects with missing or non-evaluable measurements
- All CI computed will be two-sided 95% CI

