| Invalid informed consent or fraud data (code 900) | | | |
| Study vaccine dose not administered AT ALL but subject number allocated (code 1030) | | | |
| Total vaccinated cohort | | | |
| Administration of vaccine(s) forbidden in the protocol (code 1040) | | | |
| Study vaccine dose not administered according to protocol (code 1070) | | | |
| Non compliance with blood sampling schedule (including wrong and unknown dates (code 2090) | | | |
| Essential serological data missing (code 2100) | | | |
| Obvious incoherence or abnormality or error in data (code 2120) | | | |
| ATP cohort for analysis of immunogenicity | | | |

HBV : Engerix-B challenge dose

Note: Subjects may have more than one elimination code assigned

n = number of subjects with the elimination code assigned excluding subjects who have been assigned a lower elimination code number

s = number of subjects with the elimination code assigned

% = percentage of subjects in the considered ATP cohort relative to Total vaccinated cohort

Codes are listed based on a ranking order and actual codes listed in the final will be only those applicable.

Template 5 Deviations from specifications for age and intervals between study visits (Total Vaccinated Cohort)

| GROUP | | Age | VAC_1 – SER: 2 | VAC_1 – SER: 2 |
|-----------|-------|---------------------|-------------------|--------------------|
| | | Protocol | Protocol | Protocol |
| | | from 40 to 60 years | from 5 to 12 days | from 21 to 48 days |
| HBV group | N | | | |
| | n | | | |
| | % | | | |
| | range | | | |

HBV : Engerix-B challenge dose

N = total number of subjects with available results

n/% = number / percentage of subjects with results outside of the interval

range = minimum-maximum for age and intervals

Age = Age computed at challenge dose

VAC: 1= Vaccination at visit 1

SER-2 = Blood sample collected 7 days after vaccination, SER-3 = Blood sample collected 30 days after vaccination.

Template 6 Number of subjects at each visit and list of withdrawn subjects (Total Vaccinated Cohort)

| Group | VISIT | N | Withdrawn Subject numbers | Reason for withdrawal |
|-----------|---------|---|------------------------------|-----------------------|
| HBV group | VISIT 1 | | | |
| | VISIT 2 | | | |
| | VISIT 3 | | | |

HBV : Engerix-B challenge dose

N = Number of subjects who completed the visit, Withdrawn = Subjects who did not return after the visit

Template 7 Summary of demographic characteristics (Total vaccinated cohort)

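### SAP elimination code 2120 lets an undefined judgement about the course of serology, which is the primary outcome, decide who enters the primary (ATP) analysis

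*SAP*

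**What the plan says.** SAP section 5.2.2.1 introduces its list of elimination codes with "A subject will be excluded from the ATP analysis under the following conditions". Code 2120 in that list reads "Obvious incoherence, abnormal serology evolution or error in data (incoherence between CRF and results, wrong sample labelling"). The matching row of Template 4 in SAP Annex 3 is labelled "Obvious incoherence or abnormality or error in data (code 2120").

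SAP section 6.3.1 fixes the analysis set: "The primary analysis on the response to the challenge dose will be performed on the ATP cohort for analysis of immunogenicity". SAP section 4 gives the primary endpoint as "Percentage of adult subjects with an anamnestic response 7 days and 30 days after the challenge dose". SAP section 11.2.4 defines the response. Subjects seropositive at baseline need at least a "4-fold rise in one month post-vaccination anti-HBs antibody concentrations in previously seropositive subjects". For those seronegative at baseline the rule begins "In previously seronegative subjects, anti-HBs antibody concentrations" and requires at least 10 mIU/ml at one month.

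The complementary analysis is conditional. The trigger sentence in SAP section 6.3.1 begins "If the percentage of subjects excluded from the ATP cohort for immunogenicity is more than 5%, a second analysis based on the TVC will be" and goes on to describe that analysis as a complement to the ATP one. SAP section 5.2.1 removes subjects from the TVC only under codes 1030 and 900, so a subject coded 2120 stays in it.

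**The concern.** Code 2120 joins three grounds with *or*: incoherence, an abnormal serology evolution, and error in data. The examples in brackets are data-integrity faults. They do not say what makes a course of serology abnormal. Neither document gives a threshold, names who decides, or requires the decision to be made without sight of the result or confirmed by a sample check.

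For most elimination codes this looseness would matter little. Here the course of anti-HBs from pre-challenge to one month is what the primary endpoint measures. A subject can leave the primary denominator because of the value that determines whether that subject is a responder. If such exclusions fall more often on non-responders, the reported percentage is too high and its interval too narrow and too favourable.

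Protocol section 9.4.2 requires that no elimination criterion be met, but the criteria named in sections 6.7.2 and 6.8 concern products, vaccines and medical conditions. The one serological item, anti-HBc positivity in section 6.8, is tested only at baseline (Table 10) and is not the endpoint. SAP section 9 declares no change from the planned analyses.

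**Working it through.** **Inputs.** Protocol section 9.3: 100 enrolled, 80 evaluable after 20% loss. Protocol Table 18: 76 responders of 80 as one planning row. SAP section 11.1: two-sided 95% Clopper-Pearson intervals. The number of subjects who would be coded 2120 is not in the documents; one at a time is assumed below.

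**Reproducing the plan.** 80/(1 - 0.20) = 100 enrolled. Clopper-Pearson limits for the Table 18 rows where n/80 equals the stated percentage:

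- 72/80 = 90.0% (81.2-95.6)
- 76/80 = 95.0% (87.7-98.6)
- 80/80 = 100% (95.5-100)

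All three agree with the table.

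**Effect of one exclusion.** Let x be the responders among n subjects.

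- Removing a non-responder changes the rate by x/(n - 1) - x/n = x/[n(n - 1)].
- Removing a responder changes it by (x - 1)/(n - 1) - x/n = -(n - x)/[n(n - 1)].

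With x = 76 and n = 80, n(n - 1) = 80 × 79 = 6320. The changes are 76/6320 = +1.20 percentage points and -4/6320 = -0.06 percentage points, a ratio of 76:4 = 19:1.

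| Case | Rate | Exact 95% CI |
|---|---|---|
| None removed, 76/80 | 95.0% | 87.7-98.6 |
| One non-responder removed, 76/79 | 96.2% | 89.3-99.2 |
| Two non-responders removed, 76/78 | 97.4% | 91.0-99.7 |
| One responder removed, 75/79 | 94.9% | 87.5-98.6 |

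One non-responder raises the lower limit by 89.3 - 87.7 = 1.6 points. One responder lowers it by 87.7 - 87.5 = 0.2 points.

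The 19:1 ratio is not itself a bias. If the code struck responders and non-responders with equal probability, about 19 responders would go for each non-responder and the shifts would cancel on average. Bias arises when non-responders are more likely to be coded, and nothing in the wording rules that out.

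**The TVC trigger.** With 100 vaccinated, more than 5% means six or more exclusions. The protocol expects at least 20% non-evaluable, so the trigger would probably be met.

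**The case against.** The strongest reply is that code 2120 is generic wording for data-integrity problems. The phrase sits between incoherence and error, the brackets name only CRF mismatch and mislabelling, and the neighbouring code 2070 carries an example from a Lyme study. On that reading, an abnormal profile means one that suggests swapped samples. The plan also treats non-response as an expected result: protocol section 5.7.5 describes how non-responders are handled, the reference rates in Table 19 run from 92.1% to 96.6%, and Templates 14 and 17 count responders over all subjects with both results.

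This reading is plausible, and it limits the point. A reader might infer that a flat or falling titre is what the SAP means by abnormal, so that non-responders will be removed and the estimate will be biased upward. No text says so. An implausible rise, or a reversal between Day 7 and Day 30, could equally be coded. What stands is that the phrase is a separate ground with no confirmation step, and that Template 4 keeps the same breadth.

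The second reply is that the safeguards suffice. Subjects coded 2120 stay in the TVC, that analysis will probably run, and Template 4 counts each use of the code. A reader might infer instead that five non-responders out of 100 could vanish unseen, turning 95/100 = 95.0% (88.7-98.4) into 95/95 = 100% (96.2-100). The arithmetic is right, but the case needs every exclusion in the study to be a non-responder coded 2120 and no other loss, which conflicts with the planned 20%.

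The safeguards are still partial. The TVC result only complements the ATP result, it restores all exclusions together, and it is not run at 5% or below. Template 4 shows counts, not values or responder status. Blinding the laboratory to treatment (protocol section 5.3) does not help in a single group where everyone receives the same dose.

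Third, all analyses are descriptive, so no test or success threshold can be flipped. That is correct. The consequence is confined to the primary estimate and its interval.

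**Conclusion.** The point holds as a defect of wording that leaves a route to outcome-dependent exclusion from the primary analysis. It is not evidence that such exclusion is intended or has occurred. At the plan's own 76/80, each non-responder removed adds about 1.2 points to the rate and, for the first, 1.6 points to the lower limit; a responder removed changes the rate by less than 0.1 point.

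These sizes rest on 80 evaluable subjects, a true rate near 95%, and an assumed number coded 2120. Removing all four non-responders would give 76/76 = 100% (95.3-100), but that is the arithmetic extreme, and the documents give no ground for expecting it. The change is worth making because the primary estimate rests on few non-responders and the repair is nearly free.

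**What to change.** Delete *abnormal serology evolution* from code 2120 in SAP section 5.2.2.1, and *or abnormality* from the code 2120 row of Template 4. Alternatively, keep the phrase only as a prompt for a sample or identity check, not as a ground for exclusion.

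In either case, state that a subject is excluded under code 2120 only when a sample or data error is documented independently of the anti-HBs value, for example mislabelling, a CRF and laboratory identity mismatch, or a failed assay run. Values that are unexpected but verified stay in the ATP cohort. If any subject is excluded under code 2120, also report the primary percentage with that subject included, whatever the overall exclusion rate.

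The cost is a line or two of SAP text, at most one extra row in Templates 14 and 17, slightly more analysis work, and possibly a less favourable estimate. Genuine labelling and data errors remain covered.
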